2.0 Objectives

Directions: Describe the purpose, specific aims or objectives. Be sure to also include the hypothesis being tested. 12-04-2019 Modification: Adds a 5th data collection point one year after the last described data point (the 24 week post-intervention collection point) Aim 1: Determine whether the 4-week GIFT intervention, compared to a 4-week unstructured journal-only condition, improves grandmothers' [a] mental health (general mental health and depressive symptoms), [b] physical health (self-rated and general health) and [c] family well-being (family functioning) at 2, 12, and 24 weeks post-intervention. Aim 2: Determine if changes in [a] problem solving/coping (resourcefulness), [b] resources (subjective and instrumental social support), and [c] situational appraisals (appraised stress, appraised reward, and depressive cognitions) mediate the relationships between GIFT and individual and family outcomes at 2 weeks, 12 weeks, and 24 weeks post-intervention. Aim 3. Determine if [a] grandmother demographics (age, race, education, marital status, and employment status), [b] caregiving status, and [c] family demands (intra-family strains) moderate the relationship between the intervention and the outcomes in Aims 1 and 2. **COVID-19 Supplemental Survey** – Participants who expressed an interest in future research at the 4th data collection point will be asked by phone or email to participate in a survey asking about their experiences during the covid epidemic. They will be emailed an online consent form that follows the same signing protocol we have used previously with this sample |

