family functioning, especially if the grandmother is raising grandchildren without the children's parents in the home.⁷⁻¹⁰ Most of the relevant research to date has been descriptive and focused on the stress and health risks, particularly depressive symptoms, of raising grandchildren in grandparent-headed homes, although grandmothers in multigenerational households often face complex stresses as well.¹¹⁻¹⁸ Little research, however, has examined interventions to support grandmothers during their caregiving experience. Transitions from lower levels to higher levels of grandchild caregiving (e.g., starting to raise a grandchild or initiating a multigenerational home) are associated with worsening health problems.¹⁹ During and after grandchild caregiving transitions, the presence of positive coping skills and resources, such as resourcefulness and social support, may reduce the negative effects of caregiving and family demands on the well-being of the grandmother and family.^{19,22} Our prior work links greater resourcefulness with fewer depressive symptoms and better health.^{11,23-26} We have shown that face-to-face resourcefulness training in older adults, including grandmothers, improves both mental and physical health.²⁷⁻²⁹ Our descriptive and pilot intervention studies have laid the foundation for grandparent research in the area of resourcefulness,³⁰⁻³⁴ and we propose to apply this knowledge to a widely accessible intervention that reduces stress and health risks. The purpose of this study is to extend our previously successful face-to-face resourcefulness intervention to a web-based format for grandmothers, a population with which our team has considerable experience. The web-based intervention, Grandmother Initiatives in Family Transformation (GIFT), provides online resourcefulness training using structured reflective journaling to reinforce resourcefulness skills. We will conduct a randomized clinical trial (RCT) comparing the health effects of two online conditions: GIFT vs. unstructured journaling alone. Given the limited interventions available to these groups of women, an intervention that transcends time and place and is available 24 hours a day is expected to bolster the personal and social resourcefulness of grandmothers living with and raising grandchildren, which will in turn affect individual and family health outcomes. In this two-group randomized trial, we will randomly assign 320 grandmothers to a web-based (a) GIFT resourcefulness training (n=160) or (b) an unstructured journal-only comparison group (n=160). Grandmothers' demographic characteristics, caregiving status relative to grandchildren (raising grandchildren versus sharing a home with grandchildren and their parents) and family demands (intra-family strain) will serve as covariates. Study aims are: Aim 1: Determine whether the 4-week GIFT intervention, compared to a 4-week unstructured journal-only condition, improves grandmothers' [a] mental health (general mental health and depressive symptoms), [b] physical health (self-rated and general health) and [c] family well-being (family functioning) at 2, 12, and 24 weeks post-intervention. Aim 2: Determine if changes in [a] problem solving/coping (resourcefulness), [b] resources (subjective and instrumental social support), and [c] situational appraisals (appraised stress, appraised reward, and depressive cognitions) mediate the relationships between GIFT and individual and family outcomes at 2 weeks, 12 weeks, and 24 weeks post-intervention. Aim 3. Determine if [a] grandmother demographics (age, race, education, marital status, and employment status), [b] caregiving status, and [c] family demands (intra-family strains) moderate the relationship between the intervention and the outcomes in Aims 1 and 2. Impact Based on our prior research,^{27,32} we hypothesize that the GIFT intervention will facilitate better individual and family outcomes directly, and also indirectly by reducing depressive cognitions and perceived stress, by increasing reward and support, and by buffering the effects of caregiving, family demands and demographic factors on outcomes—mechanisms that will be disentangled in this 4 year randomized trial. If our study validates our hypotheses, the GIFT intervention can provide a low-cost, readily accessible intervention to help grandmothers raising grandchildren to improve their own mental and physical well-being and thereby promote better family well-being, outcomes

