
that will have long-term individual, family, and societal benefits. Study Design We will conduct a two-group RCT with a longitudinal, multivariate design using a convenience sample of 320 grandmothers living with grandchildren age 16 or under. The RCT will compare GIFT Resourcefulness Training (video plus structured journal to practice resourcefulness skills) to the use of an unstructured journal, which has been found to have a small effect on improving stress and depressive symptoms, but significantly less than the resourcefulness intervention.^{27,52,85} We believe that no “usual care/no-care” control group is necessary to test our hypothesis, given evidence showing the relative stability of the major study variables (physical and mental health, family functioning, resourcefulness, support) over 6.5 years in [name]’s descriptive longitudinal study of grandmothers and over 18 weeks in the control group of [name]’s resourcefulness trial with grandmothers. We will extend the time of follow-up and obtain measures of outcomes, mediating variables, and potential moderating covariates at baseline/pre-intervention (T1) and 2 weeks (T2), 12 weeks (T3), and 24 weeks (T4) post intervention to evaluate early, lagged, and extended effects. |

Please add relevant references at the end of the protocol, not at the end of this section.

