16.0 Data Analysis Plan

Directions: Describe the data analysis plan, including any statistical procedures. If applicable, provide a power analysis, and study/safety endpoints. *Statistical Power Analysis for Sample Size Estimation.* For Aim 1, power analysis using G-Power⁴² for RMANOVA testing the interaction between group and time, with an alpha of .05, a power of .80 and a sample size of 250 indicates a detectable small effect size of .07, as was obtained for the social support mediators in our pilot study. The major outcome variables show much larger effects (Figure 3), and therefore, the sample size of 250 is adequate. For Aims 2 and 3, power analyses were conducted applying MacCallum, Browne, and Sugawara's¹¹⁸ calculations to determine sample size for Structural Equation Models. We use the Root Mean Square Error of Approximation (RMSEA) to assess goodness-of-fit of a hypothesized model and the sample data. In testing for power, two hypotheses (close fit and not close fit) are tested. For close fit hypotheses, the higher the power the more likely to reject an incorrect model. For not close fit hypotheses, the higher the power, the more likely to detect a reasonably correct model.¹¹⁸ The difference in two RMSEAs reflects effect size. RMSEAs of .05 (good fit) and .08 (acceptable fit) are used for close fit hypotheses, while .05 (good fit) and .01 (extremely good fit) are used for not close fit hypotheses.¹¹⁸ We constructed a multivariate cross-lagged autoregressive model with four waves of data testing how problem solving/coping, resources, and situational appraisals mediate the impact of the GIFT intervention on the individual and family well-being outcomes.^{34,55-56} Using the sample size of 250 as an estimate for a close fit hypothesis with an alpha of .05, an RMSEA1 of .05, an RMSEA2=.08, and a model with 124 degrees of freedom, the SEM had a power =.996. For a not close fit hypothesis with an alpha of .05, an RMSEA1=.05, an RMSEA2=.01, and a model with 124 degrees of freedom, the SEM had a power =.984. Thus, our final sample of 250 will provide adequate power. **Sample size and attrition.** We will enroll 167 subjects per group to achieve a sample of 125 per group at T4. While our prior longitudinal survey research had a low attrition rate (12%) over 24 months, and our web-based GIFT pilot had 92% continuation at 6 weeks, the face-to-face intervention study²⁷ had 19% loss over 18 weeks, suggesting slightly greater losses by the 24-week follow-up. Therefore, we estimate 25% attrition over the 28 week study duration (intervention plus follow-up) and plan to enroll a total of 334 subjects. Subjects tend to remain in our studies in large part due to their commitment to grandmother caregiving and the team's sensitivity to diversity, which will again be overseen by Co-I [name].

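### Section 16.0 names only an RMANOVA group-by-time test for Aim 1, inside the power calculation; a baseline-adjusted mixed model with visit contrasts would estimate the 2-, 12- and 24-week effects and usually has more power

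*Combined protocol and SAP*

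**What the plan says.** Section 16.0 (Data Analysis Plan) consists of a power analysis and an attrition paragraph. For Aim 1 it refers to "RMANOVA testing the interaction between group and time, with an alpha of .05, a power of .80 and a sample size of 250" and gives a detectable effect of .07, a size it says the pilot found for the social support mediators. It then says "The major outcome variables show much larger effects (Figure 3), and therefore, the sample size of 250 is adequate". On numbers: "We will enroll 167 subjects per group to achieve a sample of 125 per group at T4", because "we estimate 25% attrition over the 28 week study duration".

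The structural equation model in the same section is presented for Aims 2 and 3.

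Aim 1 in section 2.0 asks whether GIFT improves outcomes "at 2, 12, and 24 weeks post-intervention". The Study Design text in sections 3.0 and 12.0 says the waves are there to show early, lagged and extended effects. Section 3.0 also says that demographics, caregiving status and "family demands (intra-family strain) will serve as covariates"; the baseline value of the outcome is not in that list.

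No section states an Aim 1 analysis model, visit-specific contrasts, an analysis set or the handling of missing outcomes.

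**The concern.** The one test named does not answer the question asked. A group-by-time interaction over four waves is a single 3-df test. It can show that the arms' profiles differ, but it does not estimate the difference at 2, 12 or 24 weeks.

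If it is carried over from the power calculation into the analysis, two further costs follow. It treats T1 as one more outcome level, so the baseline is used with change-score efficiency and not as a covariate. In its classical form it also drops anyone missing a wave, so with a quarter of participants expected to be lost the result could describe four-wave completers and not those randomised.

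Because the analysis is not fixed, the choice among completers, change scores, adjusted models and contrasts could also be made after the data are seen.

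**Working it through.** **Inputs.** From section 16.0: alpha .05, power .80, N = 250 (n = 125 per arm), effect .07 and 25% attrition. From sections 2.0 and 3.0: four waves, T1 to T4. Not in the documents, so assumed: the correlation between waves (rho .3/.5/.7), the shape of the effect, the retention path, and that .07 is Cohen's f. Effects are in SD units.

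**1. The plan's own figures.** Noncentrality = f² × N × m / (1 − rho), with m = 4 and df 3 and 744. Power .80 is reached at f = .088/.074/.057 for rho .3/.5/.7, so rho = .5 is consistent with the stated .07. Taken as exactly .07, power is .59/.75/.94. Attrition: 125 / 0.75 = 166.7, hence 167 per arm and 334 in total, as stated.

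**2. Formulas for the comparison.**
- RMANOVA: (n/2) × Σ(d − d̄)² / (1 − rho) over T1 to T4, with d = 0 at T1; df 3 and 744.
- Baseline-adjusted joint test: (n/2) × d′V⁻¹d, where V is the covariance of T2 to T4 given T1; df 3 and 245.

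**3. Worked example, sustained 0.30 SD, rho .5.**
- RMANOVA: Σ(d − d̄)² = 0.75 × 0.09 = 0.0675; 62.5 × 0.0675 / 0.5 = 8.44; power .68.
- Adjusted: d′V⁻¹d = 3 × 0.09 / [(1 − .5)(1 + 3 × .5)] = 0.216; 62.5 × 0.216 = 13.5; power .88.

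**4. Results, equal correlations, rho .3/.5/.7.**

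| Effect at T2/T3/T4 (SD) | RMANOVA | Adjusted joint test |
|---|---|---|
| Sustained 0.30 | .52/.68/.90 | .86/.88/.96 |
| Fading 0.30/0.15/0, or lagged 0/0.15/0.30 | .48/.63/.87 | .60/.70/.89 |
| Sustained 0.32 (f = .07) | .59/.75/.94 | .91/.93/.98 |
| Sustained 0.50 | .94/.99/1.00 | gain at most about .06 |

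For a crossing effect (0.20/0/−0.20) the two noncentralities are equal (10.0 each at rho .5), so nothing is gained.

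**5. Decaying correlation.** Simulated AR(1) correlation of .5, .7 and .8 (RMANOVA/adjusted):
- sustained: .50/.81, .65/.87, .83/.94
- fading: .48/.65, .70/.87, .86/.97
- lagged: .47/.53, .60/.61, .72/.72

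The lagged gain can reverse slightly. A build-up of 0.1/0.2/0.3 at AR(1) .8 gave .63/.62. The lagged pattern 0/0.15/0.30, with correlation decaying by elapsed weeks, gave .74/.71.

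**6. Fading against lagged.** At rho .3/.5/.7 the RMANOVA noncentrality is 5.52/7.73/12.89 for both patterns. The adjusted joint test also has one value for both, 7.19/9.00/13.91. Neither omnibus test separates them; visit contrasts do.

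**7. Visit estimates.** The variance of a visit contrast is proportional to 1 − rho² when adjusted and 2(1 − rho) as change from baseline. The 95% half-widths are 0.24/0.22/0.18 SD against 0.29/0.25/0.19 SD.

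**8. Incomplete cases.** With assumed retention of 92/83/75%, keeping them cuts variance relative to four-wave completers by about 18% at T2, 10–11% at T3 and 1–4% at T4. If all losses come before T2, it cuts nothing.

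**The case against.** The strongest reply is that the comparison is with a method the plan has not adopted. The RMANOVA appears only in a sample-size sentence, and visit contrasts can follow an RMANOVA too. That is right as far as it goes: the criticisms of the test are conditional on its use. A reader might infer that the plan commits to a completers-only analysis. The documents do not say so; that is a property of the classical method. What remains is that nothing else is specified for Aim 1.

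A reader might also infer that the adjusted test is always stronger, or that it tells fading from lagged effects where RMANOVA cannot. Steps 5 and 6 support neither.

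The size of the gain is also open to challenge. Section 16.0 ties .07 to the social support mediators, which belong to Aim 2, and says the main outcomes show much larger effects. Figure 3 is not available here, so those sizes cannot be checked. If they are near a sustained 0.50 SD, the power gain is small. For a claim at one visit the advantage can vanish: Holm-adjusted single-visit power for sustained 0.30 SD is .61/.71/.88, below RMANOVA's .90 at rho .7.

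Finally, section 3.0 names covariates, but the Study Design text calls them potential moderators and Aim 3 uses them as such. The documents do not settle whether they adjust Aim 1.

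These points limit the power argument. They leave untouched the need for visit estimates, a stated analysis set and a missing-data rule.

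**Conclusion.** The point holds as a worthwhile, inexpensive improvement. For Aim 1 the plan names one omnibus test, in the power calculation only, and that test does not yield the effects at 2, 12 and 24 weeks.

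On the same data, a baseline-adjusted joint test raises power by .06 to .34 for a sustained 0.30 SD effect, and by about .02 to .12 for a fading or lagged one, at rho .7 down to .3 with equal correlations. The sustained and fading gains persist under AR(1) correlation. The lagged gain shrinks to nothing at about .7 to .8 and can turn slightly negative. Crossing effects gain nothing and large sustained effects little.

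A reader might conclude that the trial is underpowered. This check does not show that: the stated .07 and the enrolment of 334 both reproduce at rho .5. Correlations, effect shapes and retention are assumptions throughout.

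**What to change.** Add a paragraph to section 16.0 for Aim 1:

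- **Model.** For each outcome, a likelihood-based mixed model with T2, T3 and T4 as outcomes, the T1 value of that outcome (by visit), group-by-visit terms and unstructured covariance.
- **Analysis set.** All participants with at least one post-baseline wave, analysed as randomised.
- **Covariates.** State whether those named in section 3.0 are included. If so, use their T1 values, because they are measured again after the intervention, when GIFT may have changed them.
- **Inference.** The joint 3-df group test for each outcome, with the 2-, 12- and 24-week contrasts and 95% intervals. Apply Holm adjustment if a single visit is to support a claim.
- **Missing data.** State the missing-at-random assumption and add a shift sensitivity analysis. With 25% missing at T4, each 0.2 SD shift of the missing values in one arm moves the T4 contrast by 0.25 × 0.2 = 0.05 SD.

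No new data are needed. The costs are a little more analysis work and an assumption to defend. Participants with no post-baseline wave still contribute no outcome: about 27 of 334 if T2 retention is 92% (assumed; 0.92 × 334 = 307). Little or no power is gained for late-building or large effects. Multiplicity across the five Aim 1 outcomes is a separate matter that this change does not settle.

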
17.0 Confidentiality of Data

1. To maintain the confidentiality of the data:

I will use a unique study identifier to code individuals' identifiable data and will store the master list separate from the study data.
 I will use a unique study identifier to code individuals' data, but it will never be linked to a master list.

Other- please explain: [Click here to enter text.](#)

Provide a plan to destroy identifiers including how and when. Identifiers will be destroyed one year after study completion, in case we conduct a long term follow-up of participants. As previously approved, we cannot prevent Qualtrics from collecting IP addresses, but we will remove them from the SPSS files we save.

2. How are you storing your electronic data?

- UH Redcap
- CWRU Redcap
- CWRU Secure Research Environment (SRE)
- CWRU Box
- OnCore
- UH Secure Network Drive
- CWRU Secure Network Drive
- Other - List storage method and provide justification: Materials include the information obtained by questionnaires, journals (either structured or unstructured) using an integrated, password-protected system designed by CWRU Information Technology web designers who have consulted on the GIFT project. The system is implemented using Qualtrics and will allow participants to access all study components (video, all surveys, journals and system-related resources) at one secure site. Access to the subject's email address and phone number is necessary for this web-based study. Subject identifying data will be stored separately from other study material. Data will be collected on a firewalled, dedicated server with a backup server in the School of Nursing following established security guidelines for storing Protected Health Information. Only the research team can access the server to retrieve data. Qualtrics allows us to password-protect the entire site and allows project staff to monitor participants' journaling, and for those in the GIFT intervention group, the number of times each person viewed the GIFT training video. Participants move from the T1 baseline questionnaire, to the GIFT Resourcefulness training video for those in the GIFT intervention group, to the 4-week structured GIFT journal or the 4-week unstructured journal, to subsequent questionnaires. Participants will be able to access the site and their information 24 hours a day, 7 days a week, for the duration of the study. We have consulted with the CWRU Full INclusion of persons with Disabilities (FIND) Lab for maximizing ease of use and readability (e.g., contrast, background, font, print and graphic elements). Our Project Manager and research team will oversee that the systems are working smoothly, monitor participants' enrollment in the system and their progress on a weekly basis during the first six weeks after their enrollment, and provide email and telephone reminders. Subjects will be assured that only the study team and the Human Subjects Review Committee and staff members will have access to the information. Data stored on Box or elsewhere will not include any personal identifying information.

Please note: if you're storing or entering your electronic data in any system other than an approved system listed above, please contact the CWRU IRB ([contact]).

3. I acknowledge that paper research data and documents will be stored in a double-locked secure environment in the following **location**: Although we do not intend to keep paper research documents, any such documents would be kept in a locked office in locked files of the principal investigator.
 We will not have paper research documents.

4. Will data be shared?
 Yes

- List the exact data elements that will be shared: [Click here to enter text.](#)
- Describe how data will be sent: [Click here to enter text.](#)

 No
 N/A

(Please note: if sharing data, please contact the CWRU Tech Transfer Office to ensure the proper contracts/agreements are in place.)

18.0 HIPAA Authorization

Does this study collect, access, use, or distribute any Protected Health Information (PHI)?

Yes No

If yes, indicate how HIPAA authorization will be obtained (check all that apply):

HIPAA authorization is in the consent form
 Requesting a full or partial waiver of HIPAA for prescreening

- I will complete the Request for Waiver of HIPAA Authorization form. See *SpartaIRB Library*

 Requesting a full or partial waiver of HIPAA

- I will complete the Request for Waiver of HIPAA Authorization form. See *SpartaIRB Library*

19.0 Risks to Research Participants

1. List the reasonably foreseeable risks such as breach of confidentiality, discomforts, hazards, or inconveniences to the research participants related to their participation in the research. Include a description of the probability, magnitude, duration, and reversibility of the risks. Include the physical psychological, social, legal, and economic risks. This is a 2-group treatment trial, with subjects assigned either to GIFT Resourcefulness Training with a 4 week structured journal to reinforce skill development or to group in which women complete 4 week unstructured journals. All subjects are volunteers and non-participation and withdrawal from the study are alternatives to study participation. There are no risks to non-participation or withdrawal from the study. No physical or psychological risks other than those associated with daily living are expected for the women who participate in this study. The discomforts of completing the web surveys, journals are minimal. Reflecting on feelings or experiences of being a grandmother raising or living with and caring for a grandchild may make some women anxious, although this has not been our experience previous research; the Intervention Specialist will monitor journal content for signs of subject distress.

Participating in a research study may represent an additional time burden for grandmothers, but we expect the burden of participation to be minimal. Our project staff will be available by email or phone for procedural and technical support with the web-based pilot. Subjects who receive scores of 30 or greater on the CES- D measure of depressed mood (the cut off score for moderately depressed mood) will be referred to their primary care provider for follow-up. If it is learned that a grandchild has been a victim of any type of abuse, or is a danger to him/herself or others, then the appropriate agencies will need to be notified. Additionally, if grandmothers contact us requiring assistance of any kind we will give them United Way's First Call for Help telephone number. The First Call service provides resources on various issues such as legal matters, housing, etc. We also will have a list of local, statewide and national agencies for making necessary referrals.]

2. If applicable, indicate which experimental procedures may have risks to the research participants that are currently unforeseeable. [Click here to enter text.](#)
 N/A
3. If applicable, describe the risks to others who are not research participants. [Click here to enter text.](#)
 N/A
4. Describe the availability of medical or psychological resources that research participants might need. [Click here to enter text.](#)
 N/A

